6.1 Safety Variables

During study drug infusion: Patients will be monitored as per our standard protocol followed for a biological agent such as infliximab. The protocol is as follows:

- a. Intravenous access. Peripheral intravenous access is started for those who do not have an intravenous access. Central lines may be used for administration of intravenous fluids, medications and blood draws unless otherwise specified.
- b. Pre-medication. Acetaminophen 500 mg and diphenhydramine 25 mg will be given by mouth prior to the infusion.
- c. Infusion- related reaction medication. The following would be the medications used:
 - i. Diphenhydramine 25 mg intravenously for skin rashes
 - ii. Demerol 25 mg intravenously single dose and repeated every 15 minutes if ineffective for rigors.
 - iii. Methylprednisolone (Solu-Medrol) 1 mg/kg intravenously as a bolus for more severe infusion-related reactions like hypotension or severe bronchospasm.

Monitoring for hypersensitivity reactions: The infusions are all carried out at the clinical research center under the direction of trained personnel who have expertise in recognizing hypersensitivity reactions, as well as in treating these reactions.

Hypersensitivity reactions may also occur when the patient is at home. Preliminary studies in normal volunteers have indicated that the only possible hypersensitivity reactions noted in these patients are skin rashes. The care giver will be instructed on skin rashes and will be shown flash cards to facilitate recognition of reactions.

During follow-up: Safety will be determined based on clinical and laboratory monitoring.

Clinical: At each study follow-up visit, patients will have a physical examination with specific attention to skin changes, hypersensitivity reactions, pulmonary abnormalities, worsening in liver function as noted by increasing jaundice, ascites, or hepatic encephalopathy and presence of infection.

Laboratory: Biochemical parameters that are monitored include CRP, liver biochemistry, creatinine, and electrolytes. The study will be **stopped** if two or more patients have **either** A. AST or ALT > 500 U/L **or** B. Lille score > 0.85. The study will also be stopped if more than one patient (that is, two or more) has an adverse event grade 3 or above on the CTCAE scale that is determined to be possibly or likely attributable to study drug as per the study adjudicator. A patient will be **WITHDRAWN** from the dosing phase if Lille scores at any time are > 0.45 (treatment failure).

We recognize that determination of whether worsening of liver biochemical tests is due to the alcoholic hepatitis or study drug induced liver injury (DILI) is very difficult. An AST or ALT increase >500 IU/L would be considered an indication that the patient might have DILI since AST and ALT are typically < 250 U/L in AH. Such an increase of > 500 IU/L would trigger prompt evaluation and consideration of discontinuation of the study drug. A Lille score > 0.85 and an increase in MELD score >10 would also warrant discontinuation of the study drug. Considering how difficult it is to distinguish potential DILI from worsening of the underlying liver disease, we have incorporated an external adjudication of all suspected DILI events. This external adjudication is in addition to the data safety monitoring board (DSMB) which will monitor the entire study. A renowned hepatologist, [name], who is an internationally renowned expert both in the field of alcoholic hepatitis and DILI, has kindly agreed to serve as the external adjudicator for this IL 22 study. He will be contacted on an as needed basis when there is question of symptom causality.

The following parameters will be recorded for the safety evaluation:

- Adverse events
- Vital signs (pulse, heart rate, respiration)
- Physical examinations
- Clinical chemistry, hematology, coagulation, and urinalysis
- ECGs
- Chest X-Ray

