When AEs were assessed according to dosing, subcutaneous route at a dose of 2 $\mu\text{g}/\text{kg}$ had a delayed injection site reaction (2 mild, 4 moderate) consistent of dry skin, erythema and rash whereas IV route at a dose of 30 $\mu\text{g}/\text{kg}$ was associated with dry skin (1 moderate, 2 mild), skin allergic reaction (1 moderate), eye pruritus (1 moderate), and at a dose of 45 $\mu\text{g}/\text{kg}$ with dry skin (2 mild, 5 moderate), erythema (1 moderate), eye pruritus (1 mild, 3 moderate). Review of laboratory test results, vital signs, or ECG parameters revealed no trends or changes over time following dosing with F-652 at any dose level as either subcutaneous or IV dosing.

To characterize the PK profile, single IV infusion of F-652 or placebo was administered to four cohorts of 32 healthy male volunteers at doses of 2, 10, 30 and 45 $\mu\text{g}/\text{kg}$. Both Cmax and exposure (area under the maximum plasma concentration-time curve [AUC]0-24h) of F-652 increased proportionally with increasing doses in the dose range of 2 $\mu\text{g}/\text{kg}$ to 45 $\mu\text{g}/\text{kg}$. Tmax observed was 0.7 hr for 2 $\mu\text{g}/\text{kg}$ and 0.2 hr for 10, 30, and 45 $\mu\text{g}/\text{kg}$. The t1/2 values ranged from 39.4–206 hours and also increased with increasing dose levels. No F-652 was detected in the samples collected from control subjects.

Summary of Related TEAEs for IV Infusion Adverse Event	IV (N=40) S (%) E
Dry skin	10 (25.0%)
Eye pruritus	3 (7.5%)
Rash erythematous	2 (5.0%)
Chills	1 (2.5%)
Infusion related reaction	1 (2.5%)
Headache	1 (2.5%)
Somnolence	1 (2.5%)
Dermatitis allergic	1 (2.5%)

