1.5 Risks/Benefits

1. Beneficial Findings:

Animal studies have demonstrated that treatment with F-652 reduces ALT/AST levels in serum and TG in liver. Treatment with IL-22 adenovirus also reduces serum ALT and liver/serum TG levels. Activation of pSTAT3 was seen at 1 hr and was undetectable at 3 hrs. IL-22 induced ALT/AST/TG decreases, however, are not seen in STAT3 (hep-/-) mice. IL-22R1 expression was up-regulated in hepatocytes of alcoholic patients and ethanol-fed mice.

2. Potential Risks:

a. Overdose risk

There has been limited human experience with F-652, either at potential clinical doses or with overdose. Treatment of overdose with F-652 should consist of general supportive measures. If the symptom or sign is judged as a severe disease or disorder, treatment will be administered as per standard of care. There is no known specific antidote for overdose with F-652.

b. Warnings, precautions

There are dose-dependent increases in C reactive protein (CRP) and fibrinogen (FIB) following IV dosing with higher doses of F-652 (30 and 45 µg/kg), commencing at 12-24 hours post-dose. FIB reaches a peak at 96-120 hours post-dose; CRP may reach a peak at 48-72 hours post-dose, returning to normal 2 weeks later.

c. Hypersensitivity

The risk of hypersensitivity reactions to F-652 is unknown. If a significant hypersensitivity reaction occurs, no further doses of F-652 will be administered to that patient and appropriate treatment initiated.

d. Laboratory abnormalities

Increased serum CRP and FIB levels may be observed; these increases will be documented.

e. Local reactions at the injection site

Local injection site reactions such as erythema, dry skin and nummular eczema have occurred after the investigational product was administrated by subcutaneous injection. These changes were seen following intravenous administration at the highest dose (45 ug/kg). Local reactions generally occurred 10 to 17 days after administration of F-652, are usually were mild to moderate. Some subjects required treatment with Elocon (mometasone furoate) 0.1% cream, a moderate to strong topical corticosteroid for their skin reactions.

f. Drug interaction

The potential for drug-drug interactions with F-652 is not known.

g. Pregnancy

Adequate contraceptive methods should be used during treatment with F-652.

h. Geriatric use

There has been no geriatric experience to date.

Since no clinical data is available for F-652; any related SAE will be considered as unexpected.

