4.3 Treatment Regimen

F-652 will be administered by slow intravenous infusion over approximately 100 minutes. The study medication is reconstituted as per the protocol in 100 ml of 5% dextrose in water. To monitor, as well as prevent hypersensitivity reactions, the infusion rate will be as follows:

1. 10 ml/hr for 15 minutes
2. 20 ml/hr for 15 minutes
3. 40 ml/hr for 15 minutes
4. 80 ml/hr for 15 minutes
5. 100 ml/hr until infusion complete

That is, the total infusion will be over approximately 100 minutes. Patients will be monitored for 3 hours post-infusion with blood pressure and heart rate monitoring every 30 minutes.

CONFIDENTIAL

This material is the property of the Mayo Clinic. Do not disclose or use except as authorized.

Patients will receive two separate IV infusions separated by 6-10 days (i.e. one infusion on Day 1 and a repeat infusion approximately one week later depending on outpatient scheduling). After information is received regarding the primary end point (safety) at the first dose (10ug/kg), and the 10ug/kg dose determined to be safe, the 2nd cohort of patient will be administered the 30ug/kg dose. Further escalation will follow this scheme. If evaluations demonstrate safety and efficacy signals, patients in the final dose escalation cohort will receive a third dose of the study drug at the maximum tolerated dose on Day 14.

Medications allowed: Corticosteroids, pentoxifylline, antibiotics, acamprosate, and Baclofen, as well as any other medication deemed to be essential for the treatment of the patient will be allowed.

Prohibited medications: Biological agents and any other concomitant investigational agents.

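### Section 6.1's rash-only account of the volunteer data is not a sound basis for naming only skin rashes in the caregiver instruction; secondarily, no blood pressure or heart rate reading times are printed for the infusion itself

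*Combined protocol and SAP*

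**What the plan says.** **Volunteer experience and caregiver instruction.** In the paragraph of section 6.1 on reactions at home, the protocol says: "Preliminary studies in normal volunteers have indicated that the only possible hypersensitivity reactions noted in these patients are skin rashes". The next sentence has the caregiver taught about skin rashes, with flash cards to help recognise reactions. No other sign is named.

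**Phase I data.** The section 1.4 table of related events for intravenous dosing has rows for eye pruritus, chills and "Infusion related reaction" besides the skin events. The same section reports: "Review of laboratory test results, vital signs, or ECG parameters revealed no trends or changes over time following dosing with F-652". All treatment-emergent events were mild or moderate and none was serious.

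**Risk statement.** Section 1.5 says: "The risk of hypersensitivity reactions to F-652 is unknown". After a significant reaction, "no further doses of F-652 will be administered to that patient and appropriate treatment initiated". On late skin effects it adds: "Local reactions generally occurred 10 to 17 days after administration of F-652".

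**Infusion.** Section 4.3 introduces the rate steps with "To monitor, as well as prevent hypersensitivity reactions, the infusion rate will be as follows", and later says: "Patients will be monitored for 3 hours post-infusion with blood pressure and heart rate monitoring every 30 minutes". Section 2.1 gives the same pattern for each dosing day, with a pre-dose reading added. The schedule in 2.2 has only a row labelled Serial Vital Signs. Section 6.1 requires monitoring during infusion under the standard procedure used for a biological such as infliximab. The steps it then lists are venous access, premedication and reaction drugs.

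**The concern.** The sentence in 6.1 reports past findings, but it is placed as the reason for what caregivers are taught. If it is narrower than the data in 1.4, the instruction inherits the gap. A caregiver who has been told only about rashes may not connect chills, breathlessness or faintness at home with the study drug. The same section lists drugs for rigors, hypotension and severe bronchospasm, so staff are prepared for kinds of reaction that the caregiver instruction does not name.

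The volunteer data are also a limited guide. They come from single doses in healthy men, whereas this trial gives two or three doses to men and women with alcoholic hepatitis.

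The second issue is related. Section 4.3 gives the stepped rate a monitoring purpose, but no timed reading accompanies the steps. With approximately six sites, practice may differ if the times are not written down. What is at stake is early recognition of a reaction in an individual patient.

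**Working it through.** **Part A: the 6.1 sentence against 1.4 and 1.5**

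Inputs are the counts in the 1.4 table, whose heading gives N = 40. The stated percentages reproduce as x/40: 10/40 = 25.0%, 3/40 = 7.5%, 2/40 = 5.0%, 1/40 = 2.5%.

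| Related event (1.4) | Subjects | Skin event? | Classified as hypersensitivity? |
|---|---|---|---|
| Dry skin | 10 | yes | no |
| Rash erythematous | 2 | yes | no |
| Dermatitis allergic | 1 | yes | allergic by name; fits 6.1 |
| Eye pruritus | 3 | no | no; the text places it at 30 and 45 µg/kg IV |
| Infusion related reaction | 1 | no | no; arm and timing not given |
| Chills | 1 | no | no; arm and timing not given |

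Headache (1) and somnolence (1) are also listed; nothing here relies on them. The counts are not added, because one subject may appear in more than one row.

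1. The 6.1 wording covers *possible* reactions. An event judged drug-related and coded as an infusion related reaction is at least a candidate. The table does not show that it was hypersensitivity, and nothing in the protocol rules it out. The word *only* is therefore unsupported.
2. Precision: 1/40 has an exact 95% interval of 0.1% to 13.2%, and 3/40 of 1.6% to 20.4%. Using the 32 volunteers in the intravenous cohorts instead, the rates are 1/32 = 3.1% and 3/32 = 9.4%.
3. A reaction type never seen in n subjects has a one-sided 95% upper limit of 1 − 0.05^(1/n). This is 7.2% for n = 40 and 8.9% for n = 32. Both denominators include placebo recipients, so the limits for active drug would be higher. Even a clean volunteer record would not exclude other reactions, which agrees with 1.5 calling the risk unknown.

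**Part B: reading times against the rate steps**

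Inputs from 4.3: a 100 mL bag; 10, 20, 40 and 80 mL/hr for 15 minutes each; then 100 mL/hr to completion.

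- Volume in the first hour: 0.25 × (10 + 20 + 40 + 80) = 37.5 mL.
- Remainder: 100 − 37.5 = 62.5 mL at 100 mL/hr = 37.5 min.
- Total: 60 + 37.5 = 97.5 min, which reproduces the stated figure of approximately 100 minutes (line dead volume ignored).

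Rate increases fall at 15, 30, 45 and 60 minutes. The printed readings are pre-dose and after the end of infusion.

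- Time with no printed reading: at least 97.5 min. If the first post-infusion reading is taken 30 minutes after the end, it is 97.5 + 30 = 127.5 min.
- Generous reading: if the 30-minute interval in 2.1 is taken to run from the start of infusion, readings fall at 30, 60 and 90 min. The increases at 15 and 45 min still have none.

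These figures describe the timetable. They do not estimate how often a reaction would occur or be missed, and the protocol gives nothing from which to estimate that.

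**The case against.** **On the 6.1 sentence.** It sits in the at-home paragraph, and rash cards suit the late skin reactions described in 1.5. The contrary evidence is a few mild or moderate events, none labelled hypersensitivity. The dose-by-dose narrative in 1.4 lists neither the infusion related reaction nor the chills at 30 or 45 µg/kg, though it may be incomplete. A reader might infer that 6.1 contradicts 1.5, or that 1.4 proves a non-rash hypersensitivity reaction. Neither follows. One section reports what was noted in volunteers and the other says the risk is unknown; both can be true. The tension arises only when the first is used to limit the caregiver's instruction. That narrower point stands.

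**On caregiver training.** The cards are for recognising reactions in general and might show more than rashes, and patient-facing warnings in the consent form are not available to check. Even so, rashes are the only content the protocol names.

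**On the infusion.** A reader might infer that patients go unmonitored while the drug runs in. The protocol does not support that:

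- Section 6.1 requires monitoring during infusion, at a clinical research center, by staff trained to recognise and treat reactions. It adds premedication and named rescue drugs.
- Section 6.4 requires adverse-event questioning, with examination where appropriate, at each contact.
- Follow-up examinations look specifically for hypersensitivity and pulmonary abnormalities (6.1).
- Dosing stops after a significant hypersensitivity reaction (1.5) or a drug-attributable event of grade 3 or higher (2.7).
- Two or more patients with attributable grade 3 or higher events stop the study (6.1).

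The full infliximab-type procedure cannot be seen and may set reading times. What remains is that 6.1 presents its list as the procedure, and that list contains none. Phase I also showed no vital-sign trend, and a reading before every rate step is one convention among several.

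**Conclusion.** The point holds in a limited form. The rash-only statement in 6.1 is narrower than the related events in 1.4 (three eye pruritus, one infusion related reaction, one chills) and in tension with 1.5. It is not a sound basis for naming only skin rashes in the caregiver instruction. This does not depend on any of those events having been hypersensitivity, only on the protocol not excluding it.

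The secondary point is one of specification. No blood pressure or heart rate time is printed for the 97.5 minutes of a stepped infusion that is meant to monitor for hypersensitivity. It would fall away if the cited infusion procedure already sets those times.

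The share of the bag still to be infused at each step should not be read as an effect size. No event rate or detection probability can be derived from the protocol, and none is claimed. The primary safety analysis in 7.1 is unaffected. Low priority, but inexpensive to correct.

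**What to change.** 1. **Reword the 6.1 sentence to match 1.4 and 1.5**, for example: *After single intravenous doses in healthy volunteers, related events included skin reactions, eye pruritus, one infusion related reaction and one case of chills; the risk of hypersensitivity to F-652 is not known.*
2. **Widen the caregiver instruction.** Keep the rash flash cards and add chills or rigors, breathing difficulty, and faintness.
3. **State reading times during the infusion.** In 4.3 and the Serial Vital Signs row of 2.2, say that blood pressure and heart rate are also taken while the drug is running, preferably before rate increases, and that the rate is not increased if a reaction is suspected. If the infliximab-type procedure already sets times, citing it with those times is enough.

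**Cost.** Items 1 and 2 are wording. For item 3, 18 patients × 2 infusions = 36 infusions. A reading before each of the four increases gives 4 × 36 = 144 sets; readings at 30, 60 and 90 minutes give 3 × 36 = 108. Third doses in the expansion cohort would add to this. Staff are already present, and no visit, blood sample or ECG is added. The downside is an infusion longer than about 100 minutes when a rate step is held.

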6.2 Method and Timing

1. Adverse events, vital signs, chemistry, hematology and coagulation will be assessed at each study visit.
2. Urinalysis will be assessed at Screening.
3. ECG will be assessed at Screening, Day 7, Day 14 (if dosing) and Day 28.

6.3 Adverse Event Reporting

Definitions

Unanticipated Problems Involving Risk to Subjects or Others (UPIRTSO)

Any unanticipated problem or adverse event that meets the following three criteria:

CONFIDENTIAL

This material is the property of the Mayo Clinic. Do not disclose or use except as authorized.

- **Serious**: Serious problems or events that results in significant harm, (which may be physical, psychological, financial, social, economic, or legal) or increased risk for the subject or others (including individuals who are not research subjects). These include: (1) death; (2) life threatening adverse experience; (3) hospitalization - inpatient, new, or prolonged; (4) disability/incapacity - persistent or significant; (5) birth defect/anomaly; (6) breach of confidentiality and (7) other problems, events, or new information (i.e. publications, DSMB reports, interim findings, product labeling change) that in the opinion of the local investigator may adversely affect the rights, safety, or welfare of the subjects or others, or substantially compromise the research data, **AND**
- **Unanticipated**: (i.e. unexpected) problems or events are those that are not already described as potential risks in the protocol, consent document, not listed in the Investigator's Brochure, or not part of an underlying disease. A problem or event is "unanticipated" when it was unforeseeable at the time of its occurrence. A problem or event is "unanticipated" when it occurs at an increased frequency or at an increased severity than expected, **AND**
- **Related**: A problem or event is "related" if it is possibly related to the research procedures.

Adverse Event

An untoward or undesirable experience associated with the use of a medical product (i.e. drug, device, biologic) in a patient or research subject.

Serious Adverse Event

Adverse events are classified as serious or non-serious. Serious problems/events can be well defined and include:

- death
- life threatening adverse experience
- hospitalization
- inpatient, new, or prolonged; disability/incapacity
- persistent or significant birth defect/anomaly

and/or per protocol may be problems/events that in the opinion of the sponsor-investigator may have adversely affected the rights, safety, or welfare of the subjects or others, or substantially compromised the research data.

Other important medical events are those that may not be immediately life threatening, but are clearly of major clinical significance. They may jeopardize the subject, and may require intervention to prevent one of the other serious outcomes noted above. For example, drug overdose or abuse, a seizure that did not result in in-patient hospitalization or intensive treatment of bronchospasm in an emergency department would typically be considered serious.

All adverse events that do not meet any of the criteria for serious, should be regarded as **non-serious adverse events**.

Adverse Event Reporting Period

For this study, the study treatment follow-up period is defined as 42 days following the last administration of study treatment.

Preexisting Condition

A preexisting condition is one that is present at the start of the study. A preexisting condition should be recorded as an adverse event if the frequency, intensity, or the character of the condition worsens during the study period.

General Physical Examination Findings

At screening, any clinically significant abnormality should be recorded as a preexisting condition. At the end of the study, any new clinically significant findings/abnormalities that meet the definition of an adverse event must also be recorded and documented as an adverse event.

Post-study Adverse Event

All unresolved adverse events should be followed by the sponsor-investigator until the events are resolved, the subject is lost to follow-up, or the adverse event is otherwise explained. At the last scheduled visit, the sponsor-investigator should instruct each subject to report, to the sponsor-investigator, any subsequent event(s) that the subject, or the subject's personal physician, believes might reasonably be related to participation in this study.

Abnormal Laboratory Values

A clinical laboratory abnormality should be documented as an adverse event after the screening visit. For this study, clinically significant laboratory abnormalities will be defined as abnormal laboratory values that in the opinion of the site investigator are not explained by alcoholic hepatitis, underlying liver disease or other underlying health conditions.

All patients with laboratory tests containing clinically significant abnormal values should be followed regularly until the values return to normal ranges, until a valid reason for the AE (other than study medication related AE) is identified, or until further follow up is deemed medically unnecessary.

Hospitalization, Prolonged Hospitalization or Surgery

Any adverse event that results in hospitalization or prolonged hospitalization should be documented and reported as a serious adverse event unless specifically instructed

otherwise in this protocol. Any condition responsible for surgery should be documented as an adverse event if the condition meets the criteria for an adverse event.

Neither the condition, hospitalization, prolonged hospitalization, nor surgery are reported as an adverse event in the following circumstances:

- Hospitalization or prolonged hospitalization for diagnostic or elective surgical procedures for a preexisting condition. Surgery should **not** be reported as an outcome of an adverse event if the purpose of the surgery was elective or diagnostic and the outcome was uneventful.
- Hospitalization or prolonged hospitalization required to allow efficacy measurement for the study.
- Hospitalization or prolonged hospitalization for therapy of the target disease of the study, unless it is a worsening or increase in frequency of hospital admissions as judged by the clinical investigator.

